6. Minimal crowding 2-3 mm.

Exclusion Criteria: for the involved subjects included:

1. Patients suffering from any systemic diseases interfering with tooth movement.
2. Patients with extracted or missing permanent teeth. (Except for third molars).
3. Patients with badly decayed teeth.
4. Patients with any parafunctional habits (i.e. Bruxism, tongue thrusting, mouth breathing, etc...).
5. Patients with previous orthodontic treatment.

C] Interventions:

➤ Medical History Questionnaire:

For every patient, to exclude the presence of any systemic condition interfering with orthodontic treatment.

➤ Clinical Examination:

Oral structures will be examined to identify caries, fracture or missing teeth. Gingival tissues will be carefully examined for any gingivitis, periodontitis, recession, or lesions.

➤ Diagnosis

Check the potential patient to fulfill the previously mentioned inclusion criteria. Every participant will be asked to sign an informed consent about the study. Full set of records (study models, panorama radiograph and lateral cephalometric radiographs, photos) will be taken for every patient as part of the routine procedure for treatment of patients in the clinic of the Orthodontic Department, Future University in Egypt.

➤ Clinical Procedure:

After taking pre-treatment records, every patient will receive:

- Miniscrews will then be placed in the upper arch between the second premolar and first molar.
- The patient will be referred for extraction of first premolars.

- Anchorage will be secured, followed by Leveling and alignment for the bonded and banded teeth through following the wire sequence: 0.014 NiTi, 0.016×0.022 NiTi and 0.017×0.025 StSt.
- Bonding of all teeth except for first premolars and banding/bonding the first and second molars will be done using Roth prescription brackets (0.022 x 0.028 slot)*.
- After leveling and aligning is completed (right before retraction), the patient will be referred for the uptake of pre-intervention records for en masse group (Impression for models, photos extra oral and intra oral and pain questionnaire).
- For two step group canine retraction will take place on a 0.017×0.025 StSt arch wire, once canine retraction stage is completed, the patient will be referred for the uptake of pre-intervention records.

➤ **Acquisition of pre-intervention records:**

- Alginate impressions will be taken before retraction (without the arch wire in place) followed by digital scanning of produced models.

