- Photos (Extra and intra oral).
- Pain questionnaire distributed with explanatory session on it.

➤ **Begin of Retraction:**

- Crimpable hooks added to the arch wire (0.017"x0.025" Stainless steel) distal to the lateral incisor passing near the center of resistance of the anterior segment.
- A ligature wire extending between the second premolar and miniscrews will be used for proper anchorage control.

- Retraction will start on a 0.017"x0.025" Stainless steel wire using elastomeric chain (force applied will be 200 g per side) (24) extending between the crimpable hooks and the molar hooks.
- The force will be measured by a force gauge and reactivated every 4 weeks maintaining constant force of retraction all over the retraction phase.

➤ **Follow up visits**

Patients will be asked to attend for follow up sessions every 4 weeks for:

- Evaluation of miniscrews stability.
- Replacement of the power chain to maintain a force of 200 gm per side for en masse group and 160 gm per side for two step group.
- Impression taking to assesses amount of space closure.
- Recording the pain scoring sheet.

➤ **Criteria for discontinuing or modifying the allocated intervention:**

In cases of prolonged swelling or pain related to the miniscrew, the patient will be given strict oral hygiene measures and may wait for three weeks before the beginning of retraction.

In cases of loose or broken miniscrews, the screw will be removed and replace the miniscrew after total resolution of the inflammation.

In case of non compliant patients.

□ **Post-retraction Questionnaire:**

The patients of both groups will be asked to fill in questionnaires regarding their experience with their allocated technique, during the whole retraction period from day of extraction till the end of retraction.

□ **Retraction records**

Following en-masse and two steps retraction, patients will be referred to the same radiology center to acquire the final cone-beam CT to assess the movement and inclination of anterior teeth.

The final dental model will be used to assess the rate of retraction and molar anchorage loss achieved throughout the study.

□ **Criteria of ending the retraction**

- Class I canine relation
- Normal overjet
- Balanced facial profile
- Closing extraction space

□ **Material Used**

- American Orthodontics Brackets, Roth prescription, 22 slot size.
- American Orthodontics Elastomeric power chains
- American Orthodontics Elastomeric O-ties
- American Orthodontics Ligature wire.

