- Miniscrew, 8 mm length x 1.6mm diameter TAD (Jeil).
- American Orthodontics Arch wires.
- American Orthodontics Molar bands/tubes.

D] Outcomes

[figure not shown]
Primary outcome: is to monitor the Duration of space closure during en-masse and two steps retraction. All outcomes will be assessed as the difference between T0 at the start of retraction and T1 after complete space closure.

Secondary outcomes: is to monitor the changes in the anterior teeth position (final anterior teeth tip, torque and vertical position), anchorage loss, presence of any root resorption and pain associated with the different methods used for retraction.

E] Participant timeline:

1. The principle investigator will screen the potential patients through careful clinical examination of patients at the orthodontic department, Faculty of Oral and Dental Medicine, Future University in Egypt.
2. All recruited patients should fulfil the previously mentioned inclusion and exclusion criteria.
3. Every participant will be asked to sign an informed consent before the beginning of the study.
4. After patient's enrolment, each participant will be asked for pre-intervention records to ensure proper diagnosis.
5. The principle investigator will randomly allocate the patients to one of the intervention groups.

6. Anchorage will be secured by placement of miniscrew, followed by extraction of the first premolar.
7. Active intervention will begin after proper levelling and alignment of the upper arch.
8. The principle investigator will take pre-retraction records for every participant T0.
9. Power chain is used for anterior segment retraction.
10. Each patient will come every 4 weeks for follow up visit, for appliance activation and uptake of impression for interim records + monitoring of recording the VAS sheet.
11. After complete space closure, the principle investigator will take post-retraction records for each participant T1.
12. Every patient will fill up a questionnaire regarding his experience during treatment.
13. The principle investigator will continue the normal treatment and achieve proper finishing for every patient after the end of the study.

F] Sample size calculation:

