Our sample size calculation is based on a previous study comparing the effect of En masse versus two-steps using friction and frictionless mechanics²⁴. Using PS software output, we are planning a study of a continuous response variable from independent Group I and Group II subjects with 1 Group I(s) per Group II subject. In a previous study the response within each subject group was normally distributed with standard deviation 0.76. If the true difference in the Group II and Group I means is 1.0, we will need to study 10 Group II subjects and 10 Group I subjects to be able to reject the null hypothesis that the population means of the Group II and Group I are equal with probability (power) 0.8. The Type I error probability associated with this test of this null hypothesis is 0.05. Considering drop out a sample size 15 per group is appropriate.

G] Recruitment strategy:

The principal investigator will recruit the patients from the clinic of Orthodontic department, Faculty of Oral and Dental Medicine- Future University in Egypt. Screening of patients will continue until the total number of participants for the study is collected.

II) Assignment of interventions:

A] Sequence generation:

The supervisor of the study will apply Computer generated random numbers to randomly assign patients to group A (En-masse) or B (two steps) using Microsoft Office Excel 2007 sheet. The patient numbers will be written in the first column and the supervisor will select function RAND to generate the randomization

number in the second column. These numbers will be sorted according to the randomization number so the first column numbers will be randomly distributed.

B] Allocation concealment mechanism:

The Co-supervisor of the study ([name]) will write the randomization numbers of the patients on opaque white papers folded three times to form sealed envelopes and store it inside a box. The codes for randomization will be securely held at the secretary's office.

C] Implementation:

At the time of intervention, the main operator will send the patient to the secretary's office. Then, the assigned employee will open the box and ask the patient to select one envelope. The main operator will contact the supervisor to know the order and then the main operator will allocate each patient to assign each participant for the corresponding intervention either (En-masse or two steps group) according to the list of codes of randomization.

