Assignment to either intervention will occur before levelling and alignment stage.

D] Blinding:

Blinding of the operators: Blinding will not be possible for the operators during the application interventions and during the follow up visits. The principal operator is responsible for assigning subjects to interventions according to the concealed allocation, appliance activation at follow up visits, dental impressions and acquisition of dental casts.

Blinding of the outcome assessors: It is a single blinded study, therefore, only the outcome assessors will be blind. The patients name will be sealed from pre and

post radiographs and study models. Then two assessors will carry out, blindly and independently, the measurements and analysis of the study.

III) Data collection, management and analysis:

A] Data collection methods:

Primary outcomes:

1. Total Retraction Duration: to assess the timing of antero-posterior movement of anterior teeth and first molars, the principle investigator will take study models for every participant monthly during the follow up visits. Then will digitize the models and identify the landmarks, reference lines and planes on the pre, interim and post-retraction digital dental models for measurements reading. Also, by identifying the landmarks, reference lines and planes using CBCT taken before and after the completion of retraction.

Secondary outcome:

1. Anchorage loss: will be accessed by the principal investigator via CBCT taken before and after the completion of retraction by identifying the landmarks, reference lines and planes, then will interpret the measurements in degrees and millimeters.

2. Pain: Each patient will fill a questionnaire regarding his treatment experience in a VAS scoring from 1-10. The questionnaire will include several questions related to oral hygiene, pain and discomfort experienced throughout the trial.

B] Data management:

A colleague outside the research team will enter the data and organize it in excel sheets in the computer of the orthodontic department.

Data will include all photographs, models, radiographs and filled questionnaire.

C] Statistical Analysis:

- The principle investigator will be responsible for the extraction of the required data from the CBCT taken before and after retraction as well as the study models taken at every follow up visit. The data will be sent to a specialized statistician.

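### The primary duration is undefined for patients who do not reach closure, and no rule says how they enter the comparison

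*Combined protocol and SAP*

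**What the plan says.** All references are to the combined protocol and SAP.

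- **Outcomes (I, D):** "All outcomes will be assessed as the difference between T0 at the start of retraction and T1 after complete space closure". The Participant timeline (I, E), item 11, agrees: "After complete space closure, the principle investigator will take post-retraction records for each participant T1".
- **Sample size calculation (I, F):** 10 per group for 80% power, then "Considering drop out a sample size 15 per group is appropriate". No drop-out rate is given.
- **Criteria for discontinuing or modifying the allocated intervention (I, C):** the last entry is "In case of non compliant patients", with no action or consequence for the analysis.
- **Data collection methods (III, A):** the investigator "will take study models for every participant monthly during the follow up visits". Follow-up visits are 4-weekly.
- **Statistical Analysis (III, C):** the only two-group test is a t-test, labelled paired and described for friction versus frictionless groups, which are not this trial's arms. There is no analysis set, censoring rule or missing-data rule.

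Two definitions that the duration depends on are unsettled. In the two-step arm, "once canine retraction stage is completed, the patient will be referred for the uptake of pre-intervention records" (Clinical Procedure, I, C), whereas Outcomes places T0 at the start of retraction. The criteria for ending retraction list four conditions, of which "Closing extraction space" is only one, whereas T1 refers to space closure alone.

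**The concern.** Duration is the outcome and it also decides who has an outcome. A patient who withdraws, or whose measurement stops before closure, contributes nothing to a t-test, although dated models exist up to the last visit. Raising 10 to 15 restores numbers but does not remove selection.

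The completer comparison is sound if loss is unrelated to elapsed time, arm and the patient's own speed. If slow patients go missing from the slower arm, the difference shrinks; if from the faster arm, it grows. The operator who manages the visits is not blinded (Blinding, II, D), and nothing settles in advance how non-compliant patients are analysed.

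**Working it through.** **1. The plan's own figure.** Inputs from Sample size calculation: difference 1.0, SD 0.76, alpha 0.05, power 0.80. Two-sided testing is assumed, since sidedness is not stated.

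n per group = 2 × (1.96 + 0.84)² × 0.76² / 1.0² = 2 × 7.849 × 0.5776 = 9.07, rounded up to 10. The exact t version gives 10.12, with 79.5% power at 10. The stated 10 is reproduced. The implied allowance for loss is 1 − 10/15 = 33%.

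**2. Visit spacing.** Closure is seen only at visits 28 days (0.92 month) apart. Effective SD = √(0.76² + 0.92²/12) = √(0.5776 + 0.0705) = 0.81, so rounding to visits matters little.

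**3. Simulation.** Assumptions not in the documents: 1.0 and 0.76 are in months, mean durations are 6 and 7, and each loss mechanism is as named. There are 15 per arm, 28-day visits and 4,000 trials per row. The t-test on completers is compared with a normal interval-censored regression tested by permutation. The true difference (slower minus faster arm) is 1.0.

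| Loss | Completers: difference (power) | Censored: difference (power) |
|---|---|---|
| None | 1.00 (91.3%) | 1.00 (91.0%) |
| Random, about one-third, both arms | 1.00 (72.0%) | 1.00 (74.5%) |
| Random, slower arm only | 0.965 (78.8%) | 1.00 (82.2%) |
| Random, faster arm only | 1.04 (83.7%) | 1.00 (78.5%) |
| Common data end, 10 of 30 unclosed, 12-month entry | 0.98 (72.2%) | 0.995 (77.5%) |
| Same, 6-month entry | 0.95 (71.1%) | 1.00 (81.9%) |
| End in slower arm only, slowest 5 of 15 unclosed | 0.58 | 1.00 |
| End in faster arm only, slowest 5 of 15 unclosed | 1.42 | 1.00 |
| Slowest 6 withdraw early | 0.66 | 0.71 |
| Slowest 10 withdraw early | 0.52 | 0.64 |

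With no true difference, an end in one arm only gives false-positive rates of 27–28% for completers and 4.5–4.9% for the censored analysis. If the slowest 5 of one arm withdraw early, neither holds its level: 25% and 18%.

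**4. Robustness.** Separate code with a mean two-step duration of 8 months (800 runs per row, likelihood-ratio test) gave the same pattern, completers versus censored:

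- no loss: power 91% v 91%;
- random loss of about one-third: 73% v 75%;
- late loss in the two-step arm only: difference 0.48 v 0.98, false positives 26% v 5%;
- slow closers lost from the two-step arm only: 0.52 v 0.61, false positives 24% v 19%.

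A third run gave 72% v 76% power under random drop-out, 82% v 79% when only the faster arm drops out, and 0.64 v 0.64 when slow closers withdraw early.

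**The case against.** The strongest case against is that the large gains come from mechanisms the documents do not describe. Timeline item 11 points to follow-up of each participant to closure, and no data end is stated. Recruitment runs on ("Screening of patients will continue until the total number of participants for the study is collected"), so a common end would mostly remove late entrants. With 6 to 12 months of entry the completer bias is then 5% or less. Nothing creates a different end by arm. Under ordinary drop-out the gain is small, and if only the faster arm drops out the censored test has less power. All of this stands, and it limits the size of the point.

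Other objections stand in part. The model and permutation test are one choice among several, and heavy for a self-funded Master's project. Closed/not-closed status ignores the residual space in millimetres on the interim models. Assignment precedes levelling and alignment, so patients lost before retraction gain nothing, and restricting the analysis to those who start retraction conditions on a post-randomisation event. The supervisor does review allocation and adherence (Auditing, IV, D), but that is monitoring and not an analysis rule.

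A reader might infer that the primary result will be biased, or that non-compliant patients are removed. The documents support neither: no pattern of loss is reported, and the non-compliance entry is a fragment under a heading that covers modification as well as discontinuation. A reader might also infer that interval censoring guards against any loss that depends on duration. The figures above rule this out for withdrawal because a patient is closing slowly.

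**Conclusion.** The gap is real. As written, the plan leads to a completers-only primary comparison in a trial that allows for losing up to a third of its patients, with no rule that would limit or expose selective loss.

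The consequence depends on a mechanism that is not documented. It ranges from no bias and 2 to 4 points of power (random loss in both arms) to a true 1.0 read as 0.58 or 1.42 (a third of one arm cut off). Censoring protects against loss related to elapsed time or arm, and hardly at all against withdrawal of slow closers. It costs essentially no power when nobody is lost. These sizes assume that the plan's 1.0 and 0.76 are months, and rest on assumed mean durations and loss patterns. This is an inexpensive improvement that should be made; it is not a demonstrated fault in the result.

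**What to change.** First reconcile two things: T0 in the two-step arm, so that the clock starts in both arms before any retraction, including canine retraction; and the four ending criteria with the space-closure definition of T1, so that there is one event.

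Then state:

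- The primary analysis is time to closure from the start of any retraction, in all randomised patients who start retraction, by allocated arm, using a censored time-to-event method. Closure lies between the last 4-weekly model without it and the first with it; patients without closure are right-censored at their last model. A normal interval-censored regression giving the difference in months with a 95% confidence interval is one suitable choice. In the simulations its likelihood-ratio test was slightly liberal (5.2–7.0%), and a permutation p-value avoids this under common or arm-specific loss (3.8–5.6%), but not when slow closers withdraw early in one arm.
- An independent-samples t-test on patients with observed closure is a sensitivity analysis.
- Patients are followed to closure, including those who stop the allocated technique; otherwise state the data cut-off.
- Patients without closure, and losses between assignment and retraction, are reported by arm with reasons.
- In a delayed-closure sensitivity analysis, withdrawn patients close 0, 1 or 2 months later than the model predicts, in both arms and in each arm alone. With the slowest 6 or 10 withdrawing early, +1 month gave 1.02 or 1.07 and +2 months gave 1.33 or 1.51, so it shows sensitivity and is not a correction.

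Cost: SAP wording and two reconciled definitions. No extra visits are needed if the 4-weekly models also cover canine retraction, which the documents leave unclear. A script outside the named package may be needed. The gain is small under random drop-out, and about 3 to 5 points of power are lost if only the faster arm drops out. A right-censored log-rank test is simpler but weaker (85% v 91% with no loss).

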Outcome measure:

	Outcome Name	Measuring Tool	Measuring Unit
Primary Outcome	Duration of space closure	Dental digital Model Records of visits	
- Scanned digital models in (mm)
o Models taken every montho Analysed using 3 Shape Software- computerized record system of the recruited patient (months, days, years)

Secondary Outcomes	Anchorage loss	Digital models	- Linear measurement in mm
	Pain	Pain scoring sheets given to patients	- VAS scoring from 1-10 ^(Fig 1)

B-Research question:

Will en-masse retraction offer shorter treatment duration compared to two steps retraction, in patients having maxillary protrusion?

Objectives of the study

Research hypothesis:

The null hypothesis (H_0) of this research is that there's no difference between both en-masse and two steps techniques on duration of retraction during en-masse and two steps retraction following 1st premolar extraction.

Primary objective:

Evaluating the duration of En-masse and two steps retraction using friction mechanics.

Secondary objectives:

Assessing the amount of anchorage loss, pain and discomfort during retraction. In addition to this, of anterior teeth will be measured following en-masse and two steps retraction using friction mechanics.

Study design:

This is a randomized clinical trial with two arms parallel group, and 1:1 allocation ratio. In one group, will receive frictional mechanics during En masse retraction, while the other group will receive frictional mechanics during two steps retraction. The duration of retraction will then be compared between both interventions.

Material and Methods

I) Participants, Interventions, and Outcomes

A] Study Setting:

The study will be performed in the clinic of the Orthodontic Department at the Faculty of Oral and Dental Medicine, Future University in Egypt. The recruited sample would be from the Egyptian urban and rural population.

B] Eligibility criteria:

Inclusion criteria: for the participants include the following:

1. Age range (14-24)
2. Adolescent & Adult patients (both genders)
3. Patients with maxillary protrusion requiring first premolars extraction (Bimaxillary Protrusion or Class II division 1 cases) as confirmed from lateral cephalometric, pre-treatment records & from clinical examination.
4. Patients with fully erupted permanent teeth (not necessarily including the third molar).
5. Cases requiring maximum anchorage during retraction.

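### Read literally, the T0–T1 rule for all outcomes gives no use to the 4-weekly pain scores, the only ones recorded during retraction

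*Combined protocol and SAP*

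**What the plan says.** - **Objective.** Under Secondary objectives: "Assessing the amount of anchorage loss, pain and discomfort during retraction". The outcome table gives the tool as "Pain scoring sheets given to patients", scored 1 to 10 on a VAS.
- **Outcome rule.** I) D] Outcomes: "All outcomes will be assessed as the difference between T0 at the start of retraction and T1 after complete space closure". The paragraph that follows lists among the secondary outcomes "pain associated with the different methods used for retraction" and makes no exception for it.
- **Recording during retraction.** The 4-weekly tasks under Follow up visits include "Recording the pain scoring sheet". Item 10 of the participant timeline repeats this as "uptake of impression for interim records + monitoring of recording the VAS sheet".
- **Pre-intervention records.** These include the pain questionnaire. Under Clinical Procedure they are taken after alignment in the en-masse arm, and only after canine retraction is finished in the two-step arm.
- **End questionnaire.** Its recall window is "during the whole retraction period from day of extraction till the end of retraction".
- **Data collection and analysis.** III) A] describes pain as a VAS questionnaire on experience over the trial and names no time points. III) C] names no summary or test for the visit scores.

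**The concern.** Pain while teeth are being retracted occurs between T0 and T1. A difference between the two end points uses no score from that interval. If the rule is applied to pain as written, the analysis leaves out the measurements that address the objective, although patients complete them at every visit.

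If the rule is not applied, nothing else defines the pain outcome. The summary (mean, peak, last visit or other) could then be chosen after the data are seen.

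Two further features bear on the comparison between arms. The T0 score may be taken at a different stage of treatment in each arm. The end questionnaire covers extraction and alignment as well as retraction, and its recall period is longer in whichever arm takes longer, which ties it to the primary outcome.

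**Working it through.** The plan gives no figure for pain, and its sample-size calculation does not name pain, so there is no number to reproduce. The check compares the sections and uses simple algebra. All scores below are assumptions for illustration.

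**1. What the rule keeps.** Let P0 and P1 be a patient's VAS at T0 and T1, and let M be the mean of the visit scores between them. The rule's outcome is P1 − P0, and M does not enter it. Assume P0 = P1 = 1 in both arms, with visit scores of 3 in one arm and 5 in the other:
- T0–T1 change: 1 − 1 = 0 in each arm, so the difference between arms is 0.
- Mean during retraction: 5 − 3 = 2 points.

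**2. Whether another section rescues the visit scores.** III) A] does not mention the visit sheets under pain. III) B] keeps completed questionnaires as data but gives no analysis. In III) C] the data to be extracted are CBCT and study models, and ANOVA is assigned to the rate of anterior retraction. The t-test is a paired one, used for the group comparison (described there as friction against frictionless) and for pre/post data within groups. A last item promises an evaluation of patient acceptance without a method. None of these defines a pain summary, so the T0–T1 sentence is the only stated rule.

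**3. Whether T0 means the same in both arms.** I) D] puts T0 at the start of retraction, and the timeline makes T0 the pre-retraction records. Clinical Procedure places the corresponding records after canine retraction in the two-step arm. If those records are T0, the between-arm contrast (E for en-masse, S for two-step) is

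(P1E − P0E) − (P1S − P0S).

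With equal end scores this reduces to P0S − P0E, a contrast of baselines only. Assume visit scores of 3 in both arms, P1 = 1 in both, P0E = 1, and P0S = 3 because the canine stage has just ended:
- En-masse change: 1 − 1 = 0.
- Two-step change: 1 − 3 = −2.

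Mean pain during retraction is the same, 3 against 3, yet the change scores differ by 2 points. Step 1 hides a difference and this step creates one, so the direction of bias depends on values the documents do not give.

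**4. The recall window.** The timeline order is miniscrew and extraction, then levelling and alignment, then retraction. A window opening at extraction therefore covers phases before retraction. Suppose a recalled score gives weight w to retraction and the remainder to phases that are equally painful in both arms. A true difference of 2 points then appears as 2w: 2 × 1 = 2 at w = 1, 2 × 0.5 = 1 at w = 0.5, and 0 at w = 0. The documents do not fix w.

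**The case against.** The strongest reply is that the T0–T1 sentence is generic. It stands in the primary-outcome paragraph, where the difference between T0 and T1 is elapsed time, and it could mean only the overall assessment window. The pain-specific text describes no change score, and a plan wanting only two points would not schedule a VAS at every visit. This stands in part: the sections conflict, and the sponsor may never have intended to set the visit scores aside. But the sentence says all outcomes, pain follows without exception, and no other section offers an alternative.

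A reader might infer that the trial has no measure of pain during retraction. The documents do not support that, because the 4-weekly sheets record it. The fault is in how the outcome is defined.

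A reader might also infer that the rule pushes the comparison towards no difference. That does not follow either. T0 is not clearly before retraction force in the two-step arm, and step 3 of the working shows that a spurious difference is equally possible.

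Nor can any particular dilution be claimed for the end questionnaire. Its items are not visible, it asks about the allocated technique, and alignment is common to both arms and comes after allocation.

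Finally, changing the recall window does not remove the dependence on duration: the slower arm still recalls over a longer time.

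**Conclusion.** The point holds as a conflict between a stated outcome rule and a stated objective. Taken literally, I) D] reduces pain to a T0–T1 change and leaves the visit VAS scores without a use, and no other section defines a pain outcome. The end questionnaire does not fill the gap, since its window opens before retraction.

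The size is unknown. The 2-point effects in the working rest wholly on assumed scores and show only what the rule permits. The asymmetry between arms is conditional on the two-step pre-intervention records being T0, which the plan leaves unreconciled. The direction of any bias cannot be stated.

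The consequence is confined to one secondary outcome. The primary outcome analysis and the sample size do not depend on this point. It should be corrected before any pain data are analysed.

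**What to change.** 1. In I) D], exempt pain from the T0–T1 rule, and reconcile that section's definition of T0 with the timing of the two-step records under Clinical Procedure.
2. Define the pain outcome as each patient's mean of the 4-weekly VAS scores from first retraction force (canine retraction in the two-step arm) to complete space closure. Compare it between arms with a method for independent groups, and state this in III) A] and III) C]. A per-patient mean allows for different numbers of visits.
3. Hand out and explain the VAS sheet at the start of retraction in both arms.
4. Start the end questionnaire's recall window at first retraction force. Ask about extraction and alignment in a separate item if wanted.
5. Make the visit VAS the main pain measure, because recall length will still differ between arms. If a time-integrated total is reported, label it as dependent on duration and keep it supplementary.

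The cost is protocol wording and one changed line on the questionnaire. In the two-step arm the sheet may need to be handed out earlier than now planned, because it is unclear whether scores are collected during canine retraction. With attendance every 4 weeks, this should need no extra visits.
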